STUDY WITH TITLE:

“Investigating effects in intestinal permeability of rich in beta-glucans *Pleurotus eryngii* mushrooms fermentation supernatants: an ex-vivo study”

STUDY PROTOCOL

By using a sigmoidoscopy procedure, colon biopsies will be collected from the subjects, where the collected biopsies will be mounted in Ussing Chambers in order to investigate the effects of the fibre fractions on intestinal permeability. Collected supernatants of *Pleurotus eryngii* mushrooms will be added to the mucosal side of the biopsy together with a stressor and two permeability markers. Samples will subsequently be collected from the serosal side and will be used to measure the permeability markers related to paracellular and transcellular permeability.

STATISTICAL ANALYSIS

All statistical tests will be assessed using One Way ANOVA with a nominal significance level of 5% and post hoc testing of treatment contrasts with Tukey's HSD. The primary endpoint analysis will be based on fibre effect on the intestinal barrier function in terms of FITC passage, and whether there is a difference between treatments across all healthy subjects. Secondary endpoints include HRP quantification (supernatant), TEER values (electrophysiological parameter).

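### Does the plan's silence on how biopsies and chambers are assigned to treatments undermine the primary FITC comparison?

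*Combined protocol and SAP*

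**What the plan says.** The STUDY PROTOCOL section has the biopsies taken by sigmoidoscopy and then says that "the collected biopsies will be mounted in Ussing Chambers in order to investigate the effects of the fibre fractions on intestinal permeability". The mushroom supernatants "will be added to the mucosal side of the biopsy together with a stressor and two permeability markers", and serosal samples are drawn afterwards. Nothing is said about how a biopsy or chamber is matched to a treatment, about mounting order, or about randomisation, rotation or balance. Equally, nothing says that the order is fixed.

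Under STATISTICAL ANALYSIS, "All statistical tests will be assessed using One Way ANOVA", with "post hoc testing of treatment contrasts with Tukey's HSD". The primary question is framed "in terms of FITC passage, and whether there is a difference between treatments across all healthy subjects". No term for subject, chamber or position is named. The documents give no number of subjects, number of treatments, standard deviation or effect size.

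**The concern.** Treatment is applied to the single biopsy in its chamber, so that is the unit to be allocated. Suppose the same treatment always went into the same chamber, or always onto the first biopsy mounted, and suppose FITC passage changed with time since excision, biopsy site or chamber. Treatment and position would then be the same variable. The contrast would carry the drift as well as any fibre effect, more subjects would not shrink it, and the data could not separate the two. Allocation has to be settled before the tissue is mounted, so it cannot be repaired in the analysis. Because the primary endpoint rests on this comparison, silence on the step looks serious.

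**Working it through.** The plan has no figure to reproduce. The check asks how large the effect would be if the missing facts were unfavourable.

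**Inputs.** From the plan: one-way ANOVA, 5% level, FITC passage compared between treatments. Assumed, with nothing in the documents behind them: k = 4 treatments; n = 6, 10 or 20 subjects, each giving one biopsy per treatment; total SD 1; within-subject correlation ρ of 0, 0.3 or 0.5; linear drift of d = 0.1, 0.2 or 0.3 SD per mounting position; no true treatment effect.

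**Bias.** Under a fixed order the last-minus-first contrast is 3d = 0.3, 0.6, 0.9 SD. This restates the assumed drift. With random order within subject its expected value is 0.

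**False rejection, fixed order, ρ = 0.** The F statistic is noncentral with λ = n·d²·Σ(position − mean)². For positions 0, 1, 2, 3 the sum is 2.25 + 0.25 + 0.25 + 2.25 = 5, so λ = 5nd².

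| n | λ at d = 0.1, 0.2, 0.3 | Rejection |
|---|---|---|
| 6 | 0.3, 1.2, 2.7 | 6.5%, 11.5%, 21.1% |
| 10 | 0.5, 2.0, 4.5 | 7.8%, 17.6%, 36.2% |
| 20 | 1.0, 4.0, 9.0 | 11.2%, 34.2%, 68.6% |

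**With within-subject correlation (simulation, n = 10, d = 0.1, 0.2, 0.3).**

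| ρ | Fixed order | Random order |
|---|---|---|
| 0.3 | 3%, 11%, 30% | about 2% throughout |
| 0.5 | 1.5%, 7.5%, 25% | under 1% throughout |

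With random order and ρ = 0 the rate is 5 to 6%. The one-way test falls below 5% when ρ is positive because it leaves subject variance in its error term. The smallest drift therefore stays under 5% at n = 10 with ρ = 0.3, but is just above 5% at n = 20.

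**Is the one-way model the cause?** No. If subjects are blocked, λ becomes 5nd²/(1 − ρ). At n = 10 and ρ = 0.5 that is 1.0, 4.0, 9.0, and the blocked test rejects in 10.6%, 31.4% and 64.1% of trials, more often than the planned test. Nor could a position term help under a fixed order, since position is aliased with treatment. Only allocation matters.

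**Does rotation remove the bias?** Only if balanced. Rotating 4 treatments cyclically over 10 subjects gives two full cycles and two subjects over. In those two, the first treatment sits at positions 0 and 1 (sum 1), the third at 2 and 3 (sum 5), and the fourth at 3 and 0 (sum 3). The residual contrasts are (3 − 1)/10 = 0.2 positions for last minus first (0.02, 0.04, 0.06 SD) and (5 − 1)/10 = 0.4 positions for third minus first (0.04, 0.08, 0.12 SD).

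**The case for a change.** The strongest case for acting is that the omission is real and not a product of redaction, that it touches the primary endpoint, that the mechanism is structural, and that a sentence would close it. Absence of evidence for drift is not much comfort, because randomising or rotating is what protects against drift of unknown size, and the choice must be made before mounting.

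All of that stands as an argument for reporting the procedure. It does not show a defect in what is planned. Harm needs a fixed order and a position drift together, and the documents state neither. The calculation also needs each subject to contribute to every treatment; the plan speaks only of "whether there is a difference between treatments across all healthy subjects", which does not establish a crossed design. If the laboratory already randomises, or rotates in full balance, nothing is wrong. The figures cannot settle it either, since they run from about 1% to 69% on assumed inputs, and the bottom of that range lies below the nominal level.

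**Conclusion.** The plan leaves out how treatments are assigned to biopsies and chambers, and a fixed order combined with drift would bias the FITC contrasts beyond repair. That statement is conditional on a crossed design, a constant order and a real drift, none of which appears in the documents, and the size of any effect in this trial is unknown. No stated rule yields a wrong answer, and no stated method would be replaced by a better one: the ANOVA and Tukey contrasts would stay as they are under random or balanced allocation. This is missing bench detail that a laboratory fills at the time of mounting. It would be good to see the assignment and mounting order reported with the results, but that is a clarification and calls for no change to the plan.

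### The one-way ANOVA names no subject term and the biopsy layout is not stated; if each subject's biopsies are spread over the treatments, the test is conservative and loses power

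*Combined protocol and SAP*

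**What the plan says.** The combined protocol and SAP is short, and the relevant text is in two sections.

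- **Study Protocol.** It says "colon biopsies will be collected from the subjects, where the collected biopsies will be mounted in Ussing Chambers". The mushroom supernatants "will be added to the mucosal side of the biopsy together with a stressor and two permeability markers". The unit that receives a treatment is therefore the biopsy, and the subject is the source of biopsies.
- **Statistical Analysis.** It says "All statistical tests will be assessed using One Way ANOVA with a nominal significance level of 5" per cent, with "post hoc testing of treatment contrasts with Tukey's HSD". The primary question, on FITC passage, is "whether there is a difference between treatments across all healthy subjects". HRP and TEER are secondary and fall under the same sentence on tests.

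Neither section gives the number of subjects, treatments, biopsies per subject or replicate chambers per treatment, or the rule for assigning biopsies to treatments. Neither names a subject, block or random term, or any averaging to subject level.

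**The concern.** One-way ANOVA and Tukey's HSD treat all values as independent and judge treatment differences against a pooled within-treatment variance. If a subject supplies several biopsies and these resemble one another, that variance is generally not the right yardstick.

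The comparison across all healthy subjects fits a layout in which each subject's tissue is spread over the treatments, although it does not establish it. In that layout each subject can serve as its own control. A one-way analysis gives this up, because differences between subjects cancel from the treatment contrasts but remain in the error term. A real effect on FITC passage could then be missed, and a null result could be taken as absence of effect when the analysis was simply inefficient. The same sentence governs HRP and TEER.

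**Working it through.** The plan has no sample size, power or effect size to reproduce. Its only figure is the 5% level. All other inputs below are assumptions for illustration: n = 10 subjects, k = 4 treatments, total SD 1, one treatment shifted by 0.8 SD, within-subject correlation ρ of 0, 0.2 or 0.5.

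**1. Each subject gives one value to every treatment.** Let Vs be the between-subject variance (ρ) and Ve the residual variance (1 − ρ), with no subject-by-treatment variance. With no treatment effect:

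- expected treatment mean square = Ve
- expected one-way error mean square = Vs + Ve
- expected error mean square with subject as block = Ve

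At ρ = 0.5 the one-way F therefore compares 0.5 with 1.0, whereas the blocked F compares 0.5 with 0.5. Error degrees of freedom are 4 × 9 = 36 for one-way and 3 × 9 = 27 for blocked.

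The blocked power can be checked in closed form. With one of four treatments shifted by 0.8, the squared deviations of the treatment means sum to 0.64 × 3/4 = 0.48. The noncentrality is 10 × 0.48 / (1 − ρ), which is 4.8, 6.0 and 9.6 at the three correlations. On 3 and 27 degrees of freedom this gives power of 37%, 46% and 67%. The one-way figures are simulated.

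| ρ | One-way type I error | F power, one-way | F power, blocked | One Tukey contrast, one-way | One Tukey contrast, blocked |
|---|---|---|---|---|---|
| 0 | 5.0% | 39% | 37% | 20% | 20% |
| 0.2 | 2.4% | 35% | 46% | 18% | 26% |
| 0.5 | 0.5% | 28% | 67% | 14% | 44% |

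The blocked test holds about 5% throughout. At ρ = 0.5 the mean Tukey half-width is 1.19 SD for one-way and 0.86 SD for blocked. At the same correlation, F power is 13% against 40% with 6 subjects, and 71% against 96% with 20.

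**2. The same layout, with r replicate chambers per subject and treatment counted as independent.** Let Vst be the subject-by-treatment variance. With no treatment effect:

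- expected treatment mean square = r·Vst + Ve
- expected one-way error mean square = r(n − 1)(Vs + Vst)/(nr − 1) + Ve

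Take r = 3.

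- Vs, Vst, Ve = 0.5, 0, 0.5: treatment 0.50; error 27 × 0.5/29 + 0.5 = 0.97. Conservative; simulated type I error 0.4%.
- Vs, Vst, Ve = 0.2, 0.4, 0.4: treatment 3 × 0.4 + 0.4 = 1.60; error 27 × 0.6/29 + 0.4 = 0.96. Liberal; simulated type I error about 20%.

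The second case needs a treatment effect whose variance between subjects is twice the subject variance, which is an extreme choice. Setting the two mean squares equal gives Vst/Vs = (n − 1)/(n(r − 1)), which is 0.90 for r = 2 and 0.45 for r = 3. This is only approximate: simulation puts the 5% crossing nearer 0.8 and 0.4, because clustering also reduces the effective error degrees of freedom. A blocked F on the subject-by-treatment means holds about 5% in all these settings.

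**3. Different subjects for different treatments, several biopsies each.** Here the one-way test is liberal. With 5 subjects per treatment and 2 to 4 biopsies each, type I error is 9% to 18% at ρ = 0.2 and 17% to 40% at ρ = 0.5. Nothing in the text suggests this layout.

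**4. One biopsy per subject, or ρ = 0.** One-way ANOVA holds its level.

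**The case against.** The strongest reply is that the plan does not say a subject contributes more than one biopsy to an analysis. Biopsies and subjects are both plural, which settles nothing, and within-subject correlation is an assumption too. Silence about a subject term is also not exclusion: some authors call a one-factor repeated-measures ANOVA one-way, and values might be averaged per subject first. All of this stands. It makes the point conditional, and it is why the plan can be said only to name no subject term. It does not answer the point, because the plan states none of the conditions under which its named test would be adequate.

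A second reply is that on the likeliest layout the test errs on the safe side. That is also right. A reader might infer from the missing subject term that false positives are inflated, or that a positive FITC result could not be trusted. The documents do not support that. With one value per subject and treatment, and positive correlation, type I error is below 5%, so a significant result would be safe and the harm is lost power. The large error rates in the working need either replicates counted as independent together with strong variation in the treatment effect between subjects, or a between-subject layout for which the text gives no support.

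**Conclusion.** The point holds as a conditional one. The plan applies treatments to biopsies from subjects, names a test that assumes independence, and describes neither the layout nor the handling of subject. If each subject gives one value per treatment and these are positively correlated, the consequence is a conservative test, intervals that are too wide and lost power. In the illustration at correlation 0.5, power falls from about 67% to 28%. At correlation 0.2 the loss is smaller, 46% to 35%. These sizes rest wholly on assumed numbers of subjects and treatments, effect size and correlation.

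The direction is fixed for that layout only. With replicate chambers counted separately it could go either way. The text therefore does not show that the 5% level is breached, nor that one-way ANOVA is wrong under every layout it allows. This is a cheap improvement to the primary analysis and to both secondary ones, not a demonstrated error.

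**What to change.** State the number of biopsies per subject, the number of replicate chambers per treatment, and how biopsies are assigned to treatments. Then replace the model sentence with:

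> FITC passage, HRP and TEER will each be analysed with treatment as fixed effect and subject as block or random effect, on the mean of replicate chambers within subject and treatment; Tukey-adjusted treatment contrasts will be taken from this model.

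A random subject-by-treatment term is an alternative to averaging the replicates. If different subjects supply different treatments, analyse one mean per subject. If each subject gives exactly one biopsy, say so and keep one-way ANOVA.

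The cost is a short layout statement and one or two sentences of model wording, with no additional subjects, biopsies or measurements. The subject term uses nine error degrees of freedom in the example (27 instead of 36). If the correlation is zero, that lowers omnibus power from 38.6% to 37.4%, about one point.

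### Does leaving the measured or log scale for FITC and HRP passage unstated leave the primary test open?

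*Combined protocol and SAP*

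**What the plan says.** The STATISTICAL ANALYSIS section has three sentences. The first sets one method for every endpoint: "All statistical tests will be assessed using One Way ANOVA with a nominal significance level of 5" per cent, followed by "post hoc testing of treatment contrasts with Tukey's HSD". The second names the primary variable, "The primary endpoint analysis will be based on fibre effect on the intestinal barrier function in terms of FITC passage", and the question asked of it: "whether there is a difference between treatments across all healthy subjects". The third adds "Secondary endpoints include HRP quantification (supernatant), TEER values".

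No transformation is mentioned for FITC, HRP or TEER. No check of residuals or equal variance is described, and no alternative method is named. The section also does not say how passage is summarised (unit, time point, absolute or relative to baseline). It gives no sample size, number of treatments or SD. Nothing suggests that text was removed here.

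**The concern.** Marker passage cannot be negative and may be skewed, so a statistician would naturally ask which scale is meant. On the measured scale the F test concerns absolute differences in mean passage; on the log scale it concerns ratios. If both are taken to fit the text, the choice could be made after the results are seen.

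Three things would then be at stake: the false-positive rate of the primary test, its power, and the Tukey comparisons that show which supernatant differs. Constant variance may also hold on one scale and fail on the other, and the plan does not say what would be done in that case.

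**Working it through.** **Inputs.** From the document: alpha 5%, one-way ANOVA, Tukey's HSD. Assumed, because the document gives none of them: k = 4 treatments, n = 10 independent values each, one treatment differing, and the CVs below. There is no sample-size or power figure in the plan to reproduce.

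**Formulas.** Residual df = 4 × (10 − 1) = 36; the 5% critical value of F(3, 36) is 2.87. For lognormal data, log-scale variance = ln(1 + CV²). With one treatment shifted by δ, the noncentrality is λ = n × δ² × (3/4) / variance.

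- Log scale, 40% reduction, CV 50%: δ = ln 0.6 = −0.511; variance = ln 1.25 = 0.223; λ = 10 × 0.261 × 0.75 / 0.223 = 8.77. Power is 65%.
- Measured scale, normal data with mean 1 and an additive increase of 0.3, CV 30%: λ = 10 × 0.09 × 0.75 / 0.09 = 7.5. Power is 57%.

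Both agree with the simulation below (40,000 data sets per row, the same data analysed on each scale; a rerun agreed to within about 1 point). All entries are percentages.

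| Data and effect | CV | Power, measured | Power, log | Overall verdicts opposite | At least one of six Tukey verdicts differs |
|---|---|---|---|---|---|
| Lognormal, 40% reduction | 20 | 100 | 100 | 0 | 4 |
| | 30 | 95 | 98 | 2 | 35 |
| | 40 | 73 | 84 | 12 | 48 |
| | 50 | 49 | 65 | 18 | 43 |
| | 80 | 18 | 32 | 17 | 25 |
| Lognormal, 1.67-fold increase | 30 | 98 | 98 | 1 | 13 |
| | 50 | 65 | 65 | 9 | 28 |
| Normal, additive 30% increase | 20 | 92 | 89 | 3 | 26 |
| | 30 | 57 | 47 | 12 | 29 |
| | 35 | 44 | 32 | 14 | 26 |

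**Type I error.** With no true effect, rejection is 3.9% to 5.1% on the measured scale and 4.2% to 5.1% on the log scale. Taking the smaller p-value gives 5.4% to 6.4%. Over a wider grid of lognormal settings (3, 4 or 6 treatments; 6, 10 or 20 values each; log SD 0.3 to 1.0), the measured scale gives 3.1% to 4.9%, the smaller of two p-values 5.5% to 7.1%, and the best of three with Kruskal-Wallis added at most 8.0%.

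**Tukey error.** With the 40% reduction, the measured scale falsely separates a given pair of the three equal treatments in 1.4% to 1.8% of data sets. There are three such pairs, so the chance of any false separation is at most 3 × 1.8% = 5.4%.

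**Power.** For lognormal data at CVs of 30% to 50%, the measured scale loses 98 − 95 = 3, 84 − 73 = 11 and 65 − 49 = 16 points with the reduction, and nothing with the increase. For additive data the log scale loses 57 − 47 = 10 and 44 − 32 = 12 points at CVs of 30% and 35%.

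**Reading the Tukey column.** It counts a change in any of six verdicts, against one overall verdict. For a single truly different contrast under the lognormal reduction, the scales disagree in 13% of data sets at CV 30% (overall 3% in the same run), 20% at CV 40% (overall 12%), 18% at CV 50% (overall 18%) and 10% at CV 80% (overall 17%). Contrasts are therefore not generally more sensitive to scale than the overall test.

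**The case for a change.** The strongest case for acting is that a sentence or two would settle the scale, and that scale can matter a good deal if the data are strongly skewed. With one treatment halving passage, 4 treatments, 10 values each and a log SD of 0.6, overall power is 47% measured against 71% log, and power for one Tukey contrast is 21% against 47%. In the most skewed settings tried, the two overall verdicts differ in up to 38% of data sets. The text also never says outright that values are left untransformed.

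The arithmetic stands, and so does the omission. But these settings assume lognormal data, which favours the log scale by construction, and the document gives no sign of how skewed the data are. With additive data the preference reverses. A scale fixed without earlier assay data could therefore be the less powerful one.

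A named residual check would not help by itself. If it has no consequence it decides nothing; if it selects the analysis, it brings back the data-dependent choice it was meant to remove. Nor would fixing measured or log values close the flexibility described, since absolute and baseline-relative passage could still be exchanged.

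**Conclusion.** The observation is accurate, but it describes unwritten detail and not an error. When a plan names a variable and a one-way ANOVA and mentions no transformation, the usual reading is the variable as measured. Carried out that way, the primary test holds its 5% level in every setting examined. A published log-scale analysis would be recognisable as a departure from that reading, and an analyst who sees marked skew can show both scales openly.

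The false-positive cost of choosing freely between the scales is small: about 5.4% to 6.4% in the main settings and at most 7.1% in the wider ones, against a nominal 5%. The effect on power can be larger, but its direction depends on skewness, effect size and sample size, none of which the document gives. No better scale can be named from the text, so no change to the plan follows.

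These figures assume independent values. The document does not say whether biopsies from one subject receive several treatments. If they do, with an assumed intraclass correlation of 0.5, the one-way test without a subject term is already conservative: it rejects in about 0.5% of null data sets, and in 0.8% or less after choosing the scale. That is a separate matter from scale.

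### Does the HRP secondary endpoint measure the wrong side of the chamber because it is labelled with the word supernatant?

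*Combined protocol and SAP*

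**What the plan says.** The document has two short sections that bear on this point.

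The STUDY PROTOCOL section describes the experiment. Colon biopsies are mounted in Ussing chambers, and then: "Collected supernatants of *Pleurotus eryngii* mushrooms will be added to the mucosal side of the biopsy together with a stressor and two permeability markers". The measurement step follows: "Samples will subsequently be collected from the serosal side and will be used to measure the permeability markers related to paracellular and transcellular permeability". The two markers are not named.

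The STATISTICAL ANALYSIS section names the endpoints. The primary one is the "fibre effect on the intestinal barrier function in terms of FITC passage". The secondary ones are given in a single line, which opens "Secondary endpoints include HRP quantification (supernatant" and goes on to TEER, labelled in a parenthesis of its own as an electrophysiological parameter. No endpoint is given a compartment, a time point or a unit.

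The title also uses the word at issue, for the product being tested: "mushrooms fermentation supernatants: an ex-vivo study".

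**The concern.** A careful reader notices that supernatant already has a meaning in this document. In the title and in the protocol section it is the fermentation fluid, and the protocol section puts that fluid on the mucosal side, together with the stressor and the markers. If the word keeps that meaning in the endpoint list, HRP would be quantified in the donor fluid, while the protocol section measures the markers in the receiver fluid. The contrast with FITC adds to the doubt, because FITC is described as passage and HRP only as a quantification.

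If HRP really were assayed on the donor side, the loss would matter. Permeability is seen in what arrives on the serosal side. When only a small fraction crosses, the donor concentration is set almost entirely by the amount added, and it hardly moves even when passage doubles. A treatment effect on that marker could go unseen.

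**Working it through.** The plan gives no figure to reproduce on this point. The check compares the uses of one word with the sampling that is described, and then sizes what a donor-side assay would cost.

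**Uses of the word**

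| Place | What it refers to | Compartment stated there |
|---|---|---|
| Title | Fermentation product under test | None |
| STUDY PROTOCOL | Test fluid applied to the biopsy | Mucosal |
| STATISTICAL ANALYSIS | Parenthesis after HRP quantification | None |

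**Sampling described for the markers**

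| Side | Described? |
|---|---|
| Serosal | Yes, and stated to be for measuring the permeability markers |
| Mucosal | No |

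**Reading the two together**

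1. The protocol section has two permeability markers. The statistical section names two analytes, FITC and HRP. It is reasonable to infer that these are the two markers, although the document does not say so.
2. If HRP is a marker, the protocol section says where it is measured: "Samples will subsequently be collected from the serosal side and will be used to measure the permeability markers".
3. The statistical section does not say otherwise. It does not mention the mucosal side, the donor fluid or residual HRP. The donor-side reading appears only when the meaning of the word is carried over from the sentence about the test material.
4. That reading also lacks a sample, because no mucosal collection for the markers is described.
5. The same line attaches a parenthesis to TEER, and that one states the kind of measurement, not a place in the chamber. By parallel, the parenthesis after HRP may simply mark a fluid assay as distinct from an electrical reading. It may also point to the supernatant treatment being tested. The document does not decide between these, but neither requires a donor-side assay.

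**What a donor-side assay would cost, if it were done**

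The document gives no passage fractions, so those below are assumptions. Let a fraction *p* of the added HRP cross under control and 2*p* under treatment.

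- Receiver change = (2p − p)/p = +100% for any *p*.
- Donor change = [(1 − 2p) − (1 − p)]/(1 − p) = −p/(1 − p).

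| Assumed passage, control to treatment | Receiver change | Donor change |
|---|---|---|
| 0.5% to 1.0% | +100% | (99.0 − 99.5)/99.5 = −0.5% |
| 5% to 10% | +100% | (90 − 95)/95 = −5.3% |

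Donor fluid would therefore be a poor measure of passage across this range. Whether such changes could be detected depends on assay error, for which the document gives no value. The table shows why the compartment matters. It does not show that the plan uses the wrong one.

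**The case for a change.** The strongest case for acting is that both uses of the word with a clear meaning refer to the test fluid. No serosal sample is called a supernatant, and no step such as centrifugation is described that would produce one from serosal fluid. Both sentences are complete, so neither a redaction nor a broken table explains the mismatch. The correction would be one line and would need no new sampling. If the wording is merely loose, the text still describes the endpoint badly; if it is meant literally, the endpoint is insensitive. On either view, a tidy plan would make the two sentences agree.

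Much of this stands. The label is imprecise, and the insensitivity of the donor side is real whenever the fraction crossing is small. What does not stand is the step from an odd word to two named compartments in conflict. Only one sentence says where the markers are measured, and it says serosal. An analyst or laboratory following the document has one set of marker samples to assay and no instruction to collect another. The low cost of an edit is not a reason to require one when the measurement would be the same with or without it.

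**Conclusion.** The concern does not call for a change. The parenthesis after HRP is a loose term, and the sampling sentence in the STUDY PROTOCOL section settles how to read it: the permeability markers are measured in serosal fluid. With or without a rewording, the samples collected, the quantity assayed and the analysis stay the same, so the effect on results is nil. The point concerns a secondary endpoint only and does not touch the FITC primary endpoint.

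Two assumptions support this. The first is that HRP is one of the two unnamed markers. The second is that the sampling sentence governs its measurement, which is the natural reading because no other marker sampling is described. The small donor-side changes, about −0.5% to −5.3% for a doubling of passage under the assumed fractions, would become relevant only if HRP were actually assayed in mucosal fluid, and the plan describes no such assay.

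### TEER (secondary endpoint) has no stated time, scale or covariate; a prespecified ANCOVA on a pre-exposure reading would usually give more precise treatment contrasts than one-way ANOVA

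*Combined protocol and SAP*

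**What the plan says.** The document is a single short text with two parts, Study Protocol and Statistical Analysis.

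- **Endpoint.** Statistical Analysis lists among the secondary endpoints "TEER values (electrophysiological parameter"). TEER is not mentioned anywhere else. No time, unit or scale (absolute, change, percent of starting value) is given.
- **Model.** Statistical Analysis also states: "All statistical tests will be assessed using One Way ANOVA with a nominal significance level of 5"%. Tukey's HSD is then assigned to "post hoc testing of treatment contrasts". No covariate and no subject term is named.
- **Experiment.** Study Protocol says that "the collected biopsies will be mounted in Ussing Chambers". The mushroom supernatants "will be added to the mucosal side of the biopsy together with a stressor and two permeability markers". The only measurement step described follows this: "Samples will subsequently be collected from the serosal side and will be used to measure the permeability markers". That step yields the markers, not TEER. No TEER reading is described before or after exposure.

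**The concern.** One-way ANOVA fixes the test but not the variable that goes into it. Absolute post-exposure TEER, change from a starting value and percent of a starting value would all comply with the plan.

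The choice affects precision. Absolute values leave the stable differences between biopsies in the error term. Change scores remove them but add the noise of the starting reading. With equal variances, change improves on absolute values only when the pre/post correlation exceeds 0.5. A model with the pre-exposure reading as covariate estimates how much of that reading to subtract, instead of fixing it at none or all.

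At stake is the precision of the treatment contrasts on one secondary endpoint, and whether its definition is settled before data are seen. The FITC and HRP analyses are outside this point.

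**Working it through.** **Inputs.** From the document: one-way ANOVA, nominal 5% level, Tukey's HSD. It gives no sample size, number of treatments, biopsies per subject, standard deviation or pre/post correlation, so there is no figure of the plan's own to reproduce. Assumed here: four treatments; within-treatment pre/post correlation ρ of 0.3, 0.5 or 0.7; equal pre and post variances; random allocation of biopsies to treatments. Absolute post-exposure TEER as the comparator is also an assumption, since the plan names no scale.

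**Step 1: ANCOVA against absolute values, independent biopsies.** Let f be the error df of the one-way ANOVA (biopsies minus treatments). The expected ratio of contrast variances is

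(1 − ρ²) × (1 + 1/(f − 2)).

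| Layout (assumed) | f | ρ = 0.3 | ρ = 0.5 | ρ = 0.7 |
|---|---|---|---|---|
| 5 biopsies × 4 treatments | 20 − 4 = 16 | 0.975 | 0.804 | 0.546 |
| 10 × 4 | 40 − 4 = 36 | 0.937 | 0.772 | 0.525 |
| 20 × 4 | 80 − 4 = 76 | 0.922 | 0.760 | 0.517 |

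For example, at f = 16 and ρ = 0.5: 0.75 × 15/14 = 0.804, a fall of about 20%.

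**Step 2: ANCOVA against change scores.** The variance of change relative to the absolute value is 2(1 − ρ) = 1.40, 1.00, 0.60. At f = 16 the ratio of ANCOVA to change is 0.975/1.40 = 0.696, 0.804/1.00 = 0.804 and 0.546/0.60 = 0.911, so falls of about 30%, 20% and 9%. The ratio equals (1 + ρ)/2 × 15/14, which passes 1 at ρ = 2 × 14/15 − 1 = 0.87. Above that, ANCOVA is slightly worse than change.

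**Step 3: subject-blocked layout.** If each of 5 subjects gives one biopsy to each of 4 treatments, a model with subject has (5 − 1)(4 − 1) = 12 error df. The ratio of that model with and without the covariate is (1 − ρ²) × 1.1 = 1.00, 0.825, 0.561, where ρ is now the within-subject correlation. This comparator is not the plan's model, and no gain from the subject term is claimed.

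**Step 4: break-even with Tukey critical values.** On variance alone, break-even against no covariate is 1/√(f − 1): 0.258 at 16 df and 0.302 at 12 df. The covariate also costs one df in the Tukey critical value (four treatments, 5%).

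- 16 to 15 df: 4.046 to 4.076, squared ratio 1.0148. Break-even ρ = √(1 − 1/(1.0714 × 1.0148)) = 0.28.
- 12 to 11 df: 4.199 to 4.256, squared ratio 1.0276. Break-even ρ = √(1 − 1/(1.1 × 1.0276)) = 0.34.

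At ρ = 0.3 the squared interval width therefore changes by about −1% at 16 df and +3% at 12 df. At 36 and 76 df the correction is negligible.

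**Step 5: absolute or change within ANCOVA.** If post − pre = treatment + b × pre, then post = treatment + (b + 1) × pre. The treatment contrasts are identical on both scales, so that choice disappears. This does not extend to percent values.

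**The case against.** The strongest reply is that ANCOVA is a preference. Stating one time and one scale would close the open definition by itself. The correlation is unknown, no pre-exposure reading is described, and at ρ = 0.3 in a small experiment the gain is close to nil. Much of this stands: the gain cannot be sized from the document, it depends on a reading that may have to be added, and the 45% figure applies only against absolute values (against change at the same ρ it is 9%). What survives is that over most of the range of ρ the covariate model does better than either simple scale, and that its worst-case loss is small.

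A reader might infer that the undefined endpoint inflates the false-positive rate. If biopsies are independent and the smallest p-value over absolute, change and percent were reported, simulation gives about 9% to 10% against the nominal 5% (assumed 4 treatments, 5 to 20 biopsies each, coefficient of variation 20%). The document does not support presenting this as a property of the plan. It nowhere says such a choice will be made. Nor does it say that biopsies are independent. With one biopsy per treatment per subject, one-way ANOVA without subject is conservative, and the same smallest-p rule gives between about 0.6% and 4.9% (5 to 20 subjects, half the variance between subjects, between-/within-subject correlations 0.5/0.5 or 0.9/0.3). Inflation above 5% does not appear in those settings.

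A reader might also infer bias in the TEER comparison, or that the FITC and HRP endpoints are fully defined because they are left out here. Under random allocation only precision is affected, and this point makes no statement on how completely the other endpoints are specified.

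**Conclusion.** The point holds as a low-cost improvement to a secondary endpoint. It is documented fact that the plan states no TEER time, scale or covariate. The precision benefit is conditional: it needs a pre-exposure reading in each chamber and a correlation above about 0.28 (16 error df) or 0.34 (12 error df, subject-blocked) to improve on absolute values. Against change scores, ANCOVA is better unless the correlation is very high. At correlations of 0.5 to 0.7 and 16 df, the reduction in contrast variance is 20% to 45% against absolute values and 20% to 9% against change. All sizes rest on assumed sample sizes, four treatments, equal variances and assumed correlations. Confidence is medium, because none of these can be checked in the document.

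**What to change.** In the SAP:

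1. Define the endpoint as post-exposure TEER at one stated time. Label all other TEER summaries exploratory.
2. Record TEER in each mounted chamber before supernatant, stressor and markers go in.
3. Amend the sentence that assigns one-way ANOVA to all tests, so that TEER uses ANCOVA with treatment and pre-exposure TEER, and Tukey-adjusted contrasts of the adjusted means.
4. Add subject to that model if a subject gives more than one biopsy.
5. If no pre-exposure reading can be taken, fix the time and scale only.

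**Cost:** a few sentences, one error degree of freedom for the covariate, a small loss of precision if the correlation is below break-even, and possibly one extra recorded reading per chamber. No additional biopsy is needed.
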